### 5 STUDY OBJECTIVES AND ENDPOINTS

# 5.1 Study Objectives

## 5.1.1 Primary Objective

The primary objective of the present study is to establish the histological effects of givinostat versus placebo administered over 12 months.

# 5.1.2 Secondary Objectives

The secondary objectives of this study are the following:

- To establish the macroscopic muscle effects of givinostat versus placebo administered chronically over 12 months assessed by MRI/MRS.
- To establish the other histological effects of givinostat versus placebo administered over 12 months.
- To establish the efficacy of givinostat versus placebo administered chronically over 12 months in slowing disease progression.
- To assess the safety and tolerability of givinostat versus placebo administered chronically.
- To evaluate the pharmacokinetic (PK) profile of givinostat administered chronically in the target population.
- To evaluate the impact of givinostat versus placebo administered chronically on quality of life and activities of daily living.

### 5.1.3 Secondary Exploratory Objectives

 To evaluate the correlation between the PK profile of givinostat and pharmacodynamics (PD) data.

17 June 2020 Page 40 of 110

- To evaluate a possible disease-related biomarker.
- To explore additional disease-related MRI biomarkers.

## 5.2 Study Endpoints

## 5.2.1 Primary Endpoint

The primary endpoint of this study is the mean change in mean total fibrosis (%) comparing the histology of muscle biopsies before and after 12 months of treatment with givinostat versus placebo.

# 5.2.2 Secondary Endpoints

The secondary endpoints for this study are as follows:

- Mean change in fat fraction of vastus lateralis and soleus comparing Magnetic Resonance Spectroscopy (MRS) before and after 12 months of treatment with givinostat versus placebo.
- Mean change in fat fraction of pelvic girdle and lower limb muscles comparing Magnetic Resonance Imaging (MRI) before and after 12 months of treatment with givinostat versus placebo.
- Mean change in Cross Sectional Area (CSA) of pelvic girdle and lower limb muscles comparing MRI before and after 12 months of treatment with givinostat versus placebo.
- Mean change in other histology parameters (e.g. CSA, MFAF, regenerative fibers) comparing the histology biopsies before and after 12 months of treatment with givinostat.
- Mean change in Motor Function Measurement (MFM) before and after 12 months of treatment with givinostat versus placebo.
- Mean change in Time Function Tests (time to climb four standard steps, time to rise from floor and time to walk/run 10 m) before and after 12 months of treatment with givinostat versus placebo
- Mean change in 6 Minute Walking Test (6MWT) before and after 12 months of treatment with givinostat versus placebo.
- Proportion of patients with < 10% worsening in 6MWT at the end of study.

- Proportion of patients who lose the ability to rise from floor (Baseline through end of study).
- Proportion of patients who lose ambulation during the study.

17 June 2020 Page 41 of 110

- Mean change in muscle strength evaluated by knee extension, elbow flexion as measured by Hand Held Myometry (HHM), before and after 12 months of treatment with givinostat versus placebo.
- Mean changes in quality of life (assessed by the 36-item Short Form survey [SF36]) before and after 12 months of treatment with givinostat as compared to placebo.

## 5.2.3 Safety Endpoints

The safety endpoints of this study are as follows:

- Number of patients experiencing treatment-emergent adverse events (TEAEs) and serious adverse events (SAEs) from Baseline through end of study (EOS).
- Type, incidence, and severity of TEAEs and SAEs (Baseline through EOS).
- Changes from baseline to end of study of:
  - Vital signs and clinical laboratory tests (blood chemistry and hematology).
  - Physical examination.
  - Pulmonary function evaluated by Forced Vital Capacity (FVC), Forced Expiratory Volume at 1 second (FEV1), FVC/FEV1, Peak Expiratory Flow (PEF).
  - Cardiac function evaluated by ECG and ECHO.
  - Weight, height, and body mass index (BMI).

## 5.2.4 Pharmacokinetic Endpoints

The PK endpoints of this study are as follows:

Description of the PK of givinostat and its major metabolites: ITF2374 and ITF2375.

## 5.2.5 Exploratory Endpoints

The exploratory endpoints of this study are the following:

- PK-PD analyses of the relationship between metrics of exposure and the efficacy/safety endpoints of givinostat.
- Analyses to explore whether the effects of givinostat versus placebo administered chronically may be related to the type of LTBP4 or Osteopontin genotype.
- Evaluation of serum circulating proteins, by an ELISA based system, as potential biomarkers for BMD.
- Additional evaluations of other muscle image parameters assessed by MRI (details will be provided in a specific imaging protocol).

17 June 2020 Page 42 of 110

### 6 INVESTIGATIONAL PLAN

# 6.1 Description of Overall Study Design and Plan

This is a Phase 2, randomised, double-blind, placebo-controlled study. Ambulant patients who have provided written informed consent will undergo a 4-week screening period to determine eligibility for the study. Approximately 48 eligible patients will then be randomized in a 2:1 ratio to be treated with givinostat or placebo for a period of 12 months. The randomization process will be stratified by the factor related to concomitant steroid use at baseline (yes vs. no). Patients who complete the study (i.e. 12 months of treatment) will be asked to return for a follow-up visit 4 weeks after the end of treatment.

An overview of the study is provided in Figure 1.

Figure 1: Study Design

A total of 12 visits will take place during the study: Screening (V1, V2), Randomization (V3), Treatment (V4-V10), End of Study (V11) and Follow-up (V12). Visits during the treatment period will take place every 12 weeks except for the first 2 months, when they will occur every 2 weeks to allow close monitoring of hematological safety parameters. Patients may be evaluated more often if necessary, for safety reasons. Patients who discontinue the study treatment early will be asked to come in for an Early Withdrawal Visit within 4 weeks

17 June 2020 Page 43 of 110

after the last dose of study treatment. Patients who have ongoing AEs at discontinuation will be followed until resolution or stabilization.

# 6.2 Discussion of Study Design

This study has been designed as a conventional parallel-group design. Since the study will be conducted in a population with a serious and life-threatening disease, the unequal randomization ratio (2:1 givinostat vs. placebo) will be applied to reduce the exposure to placebo. A 2:1 randomization also provides for an increased number of patients who are exposed to givinostat. The randomization process will be stratified by the factor related to concomitant steroid use at baseline (yes vs. no).

Considering a 5% of unevaluable baseline biopsies, 51 patients will be randomized in the study to have 48 fully evaluable patients.

After the first 20 baseline muscle biopsies were collected, a blinded interim analysis was planned, aimed at checking the variability of the original primary endpoint (i.e. CSA). The observed variability of the original primary endpoint was very large, leading to a revision of the primary endpoint to % total fibrosis. The sample size was amended accordingly to require a total of 51 patient to be randomized on a 2:1 basis.

#### 7 SELECTION AND WITHDRAWAL OF PATIENTS

The study will enroll adult male patients with an established molecular diagnosis of BMD.

Specific entry criteria are detailed in Section 7.1 and in Section 7.2.

At the discretion of the Investigator, patients not meeting inclusion/exclusion criteria may be re-screened twice with an interval of at least 30 days between assessments.

Patients dropping out before the end of treatment will not be replaced.

### 7.1 Inclusion Criteria

Patients must meet all of the following criteria in order to be included in the study:

- Ambulant male patients aged ≥18 years to ≤ 65 years at randomization with BMD diagnosis confirmed by genetic testing.
- Able and willing to give informed consent in writing.

17 June 2020 Page 44 of 110

- Able to perform 6MWT at screening with a minimum distance of 200 m and maximum distance of 450 m.
- 4. If in treatment with systemic corticosteroids and/or ACE inhibitor, and/or  $\beta$  or  $\alpha$  adrenergic receptor blocker, no significant change in dosage or dosing regimen (excluding changes related to body weight change) for a minimum of 6 months immediately prior to start of study treatment.
- 5. Patients must be willing to use adequate contraception. Contraceptive methods must be used from Randomization through 3 months after the last dose of study treatment, and include the following:
  - True abstinence (absence of any sexual intercourse), when in line with the
    preferred and usual lifestyle of the patient. Periodic abstinence (e.g. calendar
    ovulation, symptothermal, post ovulation methods) and withdrawal are not
    acceptable methods of contraception.
  - Condom with spermicide and the female partner must use an acceptable method
    of contraception, such as an oral, transdermal, injectable or implanted steroidbased contraceptive, or a diaphragm or a barrier method of contraception in
    conjunction with spermicidal jelly such as for example cervical cap with
    spermicide jelly.

### 7.2 Exclusion Criteria

Patients meeting any of the following criteria are ineligible to participate in this study:

- Exposure to another investigational drug within 3 months prior to the start of study treatment.
- Use of any pharmacologic treatment, other than corticosteroids, that might have an
  effect on muscle strength or function within 3 months prior to the start of study
  treatment (e.g., growth hormone). Vitamin D, calcium, and any other supplements
  will be allowed.
- Surgery that might have an effect on muscle strength or function within 3 months before study entry or planned surgery at any time during the study.
- 4. Presence of other clinically significant disease that in the Investigator's opinion could adversely affect the safety of the patient, making it unlikely that the course of treatment or follow-up is completed, or could impair the assessment of study results.
- A diagnosis of other uncontrolled neurological diseases or presence of relevant somatic disorders not related to BMD that may interfere with the ability to perform the muscle function tests and/or to comply with the study protocol procedures.

17 June 2020 Page 45 of 110

- Platelet count, White Blood Cell (WBC) count and hemoglobin at screening < Lower Limit of Normal (LLN). If laboratory screening results are < LLN, platelet count, WBC count and hemoglobin are to be repeated once, and if again < LLN become exclusionary.
- Symptomatic cardiomyopathy or heart failure (New York Heart Association Class III or IV) or left ventricular ejection fraction < 50% at screening or with heart transplant.

- Current liver disease or impairment, including but not limited to elevated total bilirubin (> 1.5 x ULN), unless secondary to Gilbert's disease or pattern consistent with Gilbert's disease.
- Inadequate renal function, as defined by serum Cystatin C > 2 x the upper limit of normal (ULN). If the value is > 2 x ULN, serum Cystatin C will be repeated once, and if again > 2 x ULN becomes exclusionary.
- Positive test for hepatitis B surface antigen, hepatitis C antibody, or human immunodeficiency virus at screening.
- Baseline corrected QT interval, Fredericia's correction (QTcF) > 450 msec, (as the mean of 3 consecutive readings 5 minutes apart) or history of additional risk factors for torsades de pointes (e.g., heart failure, hypokalemia, or family history of long QT syndrome).
- Current psychiatric illness/social situations rendering the potential patient unable to understand and comply with the muscle function tests and/or with the study protocol procedures.
- Hypersensitivity to the components of study medication.
- Sorbitol intolerance or sorbitol malabsorption, or the hereditary form of fructose intolerance.
- Contraindications to muscle biopsy.
- Contraindications to MRI/MRS (e.g., claustrophobia, metal implants, or seizure disorder).
- Hypertriglyceridemia (> 1.5 x upper limit of normal [ULN])\*
  - \*At screening, patients with hypertriglyceridemia can be enrolled if in stable treatment and with controlled levels of triglycerides (i.e. within normal range) for at least six months.

### 7.3 Withdrawal and Removal of Patients

Withdrawal from study participation and study medication may occur under the following circumstances:

17 June 2020 Page 46 of 110

- Withdrawal of consent: The patient desires to withdraw from further participation in the study in the absence of the Investigator determining a medical need to withdraw.
   If the patient gives a reason for withdrawing, it should be recorded in the electronic Case Report Form (eCRF).
- Protocol Violation: The patient's findings or conduct fails to meet the protocol entry criteria
- Lost to Follow-Up: The patient stopped coming for visits, and study personnel were unable to contact the patient (at least 3 contact attempts should be documented).
- Other reason: The patient was discontinued for a reason other than those listed above, such as at the discretion of the Investigator (i.e., any other condition that, in the opinion of the Investigator, may jeopardize the study conduct according to the protocol, or when the Investigator feels that it is in the best interest of the patient to discontinue) or termination of study by the Sponsor.

Withdrawal from study medication may occur under the following circumstance:

Adverse event: Clinical or laboratory events occur that, in the medical judgment of
the Investigator for the best interest of the patient, are grounds for discontinuation.
Moreover, if the patient meets one of the safety stopping criteria described in Section
7.3.1, he will be withdrawn from the study medication. In case of withdrawal due to
AEs/SAEs, the Investigator will follow up the patient until resolution or acceptable
stabilization of the event and document all the relevant information, as applicable.

Before withdrawing a subject, each case can be discussed with the study medical monitor, but the final decision remains with the Investigator only or authorized designee. If the safety of the subject can be reasonably assured, the subject will not be discontinued.

In case of withdrawal from study participation and /or study medication, the following general rules apply:

- If a patient is discontinued from study medication and is withdrawn from the study for any reason, the study site must immediately notify the medical monitor.
- When a patient withdraws from the study, the date and reasons for withdrawal shall be recorded by the Investigator on the patient's medical file and on the relevant page of the eCRF. In case of multiple reasons, AEs should be indicated as the primary reason whenever applicable. All relevant information related to the reason for

17 June 2020 Page 47 of 110

treatment discontinuation including contributory factors must be included on the eCRF.

- All patients prematurely discontinuing the study must be seen for a final evaluation
  performed within 4 weeks after the last drug intake. Final evaluation is defined as
  completion of the assessments scheduled for the Early Withdrawal Visit (as detailed
  in Section 9.1.10). Data collected during the final evaluation are crucial to the
  integrity of the final study analysis because early withdrawal may be related to the
  safety profile of the study drug. The Investigator will make every effort to see patients
  who fail to return for a final visit.
- If a patient is discontinued prematurely from the study due to a treatment-related TEAE or serious TEAE, the TEAE or serious TEAE will be followed until it resolves (returns to normal or baseline values) or stabilizes, or until it is judged by the Investigator to be no longer clinically significant.

Once a patient is withdrawn from the study, he may not re-enter it.

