### Safety endpoints:

- Number of patients experiencing treatment-emergent adverse events (TEAEs) and serious adverse events (SAEs) from Baseline through end of study (EOS).
- Type, incidence, and severity of TEAEs and SAEs (Baseline through EOS).
- Changes from baseline to end of study of:
  - Vital signs and clinical laboratory tests (blood chemistry and hematology).
  - Physical examination.
  - Pulmonary function evaluated by Forced Vital Capacity (FVC), Forced Expiratory Volume at 1 second (FEV1), FVC/FEV1, Peak Expiratory Flow (PEF).
  - Cardiac function evaluated by ECG and ECHO.
  - Weight, height, and body mass index (BMI).

17 June 2020 Page 8 of 110

	Pharmacokinetic endpoints
	
 
Description of the PK of givinostat and its major metabolites: ITF2374 and ITF2375.
 

	
 
Exploratory endpoints:
 
PK-PD analyses of the relationship between metrics of exposure and the efficacy/safety endpoints of givinostat.
 
Analyses to explore whether the effects of givinostat versus placebo administered chronically may be related to the type of LTBP4 or osteopontin genotype.
 
Evaluation of serum circulating proteins, by an ELISA based system, as potential biomarkers for BMD.
 
Additional evaluations of other muscle image parameters assessed by MRI (details will be provided in a specific imaging protocol).
 

Rules for cessation of randomised treatment in an individual participant:	The Study treatment should be permanently discontinued if any of the following events occur:  • Severe drug-related diarrhea (increase of ≥ 7 stools per day)  • Any drug-related SAE  • QTcF > 500 msec  • Platelet count ≤ 50 x 10  /L (see protocol for details)
	
 
White blood cell count ≤ 2.0 x 10^9/L (see protocol for details)
 
Hemoglobin ≤ 8.0 g/dL (see protocol for details)
 

Rules for temporary interruption of randomised treatment in an individual participant and dose modification	The Study treatment should be temporarily interrupted if any of the following events occur, see protocol for details:  • Moderate or severe diarrhea (increase more than 4 stools/day).  • Platelet count < 75 x 10  /L but > 50 x 10  /L.  • White blood cell < 3.0 x 10  /L but > 2.0 x 10  /L.  • Hemoglobin < 10.0 g/dL but > 8.0 g/dL  • Triglycerides >300 mg/dL*

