# 7.3.1 Safety Stopping Rules

The study treatment should be permanently discontinued if any of the following events occur:

- Severe drug-related diarrhea (increase of ≥ 7 stools per day).
- Any drug-related SAE.
- QTcF > 500 msec\*.
- Platelet count ≤ 50 x 10^9/L. To avoid laboratory errors and anomalous values, a
  platelet count ≤ 50 x 10^9/L must be confirmed with a repeated test performed on the
  next working day. Treatment should be stopped until the retest result becomes
  available. If the repeated platelet count is still ≤ 50 x 10^9/L, study treatment must be
  permanently discontinued. If the repeated test is acceptable, the patient can resume
  treatment.
- White blood cell count ≤ 2.0 x 10^9/L. To avoid laboratory errors and anomalous values, white blood cells ≤ 2.0 x 10^9/L must be confirmed with a repeated test performed on the next working day. Treatment should be stopped until the retest result becomes available. If the repeated white blood cells count is still ≤ 2.0 x 10^9/L, study treatment must be permanently discontinued. If the repeated test is acceptable, the patient can resume treatment.
- Hemoglobin ≤ 8.0 g/dL. To avoid laboratory errors and anomalous values, hemoglobin ≤ 8.0 g/dL must be confirmed with a repeated test performed on the next

17 June 2020 Page 48 of 110

working day. The treatment should be stopped until the retest result becomes available. If the repeated hemoglobin is still  $\leq 8.0$  g/dL, study treatment must be permanently discontinued. If the repeated test is acceptable, the patient can resume treatment.

The Investigator will follow up until resolution or acceptable stabilization of the event and document all the relevant information, as applicable. After the resolution/stabilization of the event, the patient will be withdrawn from the study and the EOS Visit (see Section 9.1.10) will be performed.

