\* Based on average QTc value of triplicate ECGs. For example, if an ECG demonstrates a prolonged QT interval, 2 more ECGs should be obtained over a brief period, and then the averaged QTcF values of the 3 ECGs should be used to determine whether the patient should be discontinued from the study. If the mean QTcF value of the 3 replicates still meets the stopping criteria, the patient has to interrupt the study treatment, the medical monitor has to be informed and the value must be confirmed by central reading before withdrawing the patient from the study. The QTc has to be calculated with the Fridericia formula QTc = QT/RR1/3.

The Study treatment should be temporarily interrupted if any of the following events occur:

- Moderate or severe diarrhea (increase more than 4 stools per day).
- Platelet count < 75 x 10^9/L but > 50 x 10^9/L (treatment should be temporarily stopped, and the platelet count repeated within 1 week and retested until platelets are normal).
- White blood cell < 3.0 x 10^9/L but > 2.0 x 10^9/L (treatment should be temporarily stopped, and white blood cells re-measured within 1 week and retested until white blood cells are normal).
- Hemoglobin < 10.0 g/dL but > 8.0 g/dL (treatment should be temporarily stopped, and hemoglobin re-measured within 1 week and retested until hemoglobin is normal).
- Triglycerides > 300mg/dL (see also section 8.8)

The study treatment can be reduced by 20% of the current dose at which the AE leading to temporary interruption occurred, once platelets and/or white blood cell and/or hemoglobin and/or triglycerides are normalized, or diarrhea is mild. See Section 8.2.2 for more details.

The patient may have unscheduled visits if needed until the AE resolves, and will then continue the study as per scheduled visits. Further procedures (blood sample collection) may also be performed by a qualified trained nurse at the patient's home.

17 June 2020 Page 49 of 110

In addition, if a patient has a consistent (at least two consecutive evaluations) platelet count  $\leq$  150 x 10^9/L that does not meet stopping criteria for platelets, the Investigator will have to reduce the dose by 20% of the current dose. See Section 8.2.2 for more details.

Hematology parameters will be evaluated every 2 weeks during the first 2 months of treatment (Visits 4-7) to closely monitor these safety parameters.

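### Protocol 7.3 and 8.4 keep a patient from being discontinued when safety is judged assured, with no exception for the 7.3.1 stopping criteria, so the same confirmed event can be handled in opposite ways

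*Protocol*

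**What the plan says.** The rule on permanent stopping appears in four places in the protocol.

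- **Synopsis, rules for cessation of randomised treatment:** "The Study treatment should be permanently discontinued if any of the following events occur". The list in 7.3.1 opens with the same *should*.
- **Section 7.3, adverse-event reason for withdrawal:** if a patient meets one of the 7.3.1 criteria, "he will be withdrawn from the study medication". This covers every criterion on the list.
- **Section 7.3.1:** there are six permanent-stop criteria: severe drug-related diarrhea, drug-related SAE, QTcF above 500 msec, and low platelets, white cells or hemoglobin. For the three blood counts, once a repeat test confirms the value, "study treatment must be permanently discontinued". After the event resolves or stabilizes, "the patient will be withdrawn from the study and the EOS Visit" is performed.
- **Section 7.3, next paragraph, and section 8.4:** a case may be discussed with the medical monitor before a patient is withdrawn, but "the final decision remains with the Investigator only or authorized designee". Then: "If the safety of the subject can be reasonably assured, the subject will not be discontinued".

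No section says which of these takes precedence.

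**The concern.** One section gives two directives for the same patient. One says that meeting a listed criterion ends study medication. The other says that a patient whose safety can be reasonably assured is not discontinued, and it follows directly after the sentence that invokes 7.3.1. An investigator facing a confirmed event can cite either.

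Two things are at stake. The first is the safeguard itself. The 7.3.1 list is the protocol's rule for ending an individual's treatment, and platelet effects have been common in this trial. Amendment 2 reports that 11 of 21 blinded patients needed a dose reduction at the earlier, higher starting dose, three of them with a temporary interruption.

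The second is the data. Permanent discontinuations and their reasons are planned outputs (Protocol 13.4), summarized by treatment group (SAP 6.4.1), as are adverse events leading to withdrawal of treatment (SAP 6.4.3). If identical events can be handled differently, those counts partly reflect how each investigator read 7.3. Stopping also changes the efficacy record. Protocol 9.1.10 does not require MRI/MRS at an early withdrawal visit, and the SAP (1.1) calls MRI a key secondary endpoint. The closing biopsy is still due, but earlier than month 12.

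**Working it through.** The plan states no figure on this point, so the check is a comparison of the texts.

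1. **How binding is each criterion?** The list is introduced with *should* in both the synopsis and 7.3.1. *Must* is attached only to confirmed platelet, white cell and hemoglobin values. For drug-related diarrhea, "Any drug-related SAE" and QTcF, the binding word is the *will* in 7.3. So all six criteria are binding through 7.3, and three of them also through 7.3.1. The conflict is therefore partly internal to 7.3.

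2. **Which events are in question?** Only confirmed ones. The blood counts need a repeat test on the next working day. QTcF uses the mean of three ECGs, and "the value must be confirmed by central reading before withdrawing the patient from the study". These steps establish that the event is real. They do not settle what follows.

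3. **What does *discontinued* mean in the disputed sentence?** The protocol uses the word both ways. The general rules in 7.3 speak of discontinuation from study medication and also of discontinuing the study, and the QTcF footnote in 7.3.1 speaks of discontinuation from the study.
   - If it means study treatment, the sentence conflicts with "he will be withdrawn from the study medication" in 7.3 and, for the three blood counts, with "study treatment must be permanently discontinued" in 7.3.1.
   - If it means study participation, it conflicts with 7.3.1, where "the patient will be withdrawn from the study and the EOS Visit" is performed once the event has settled. The dosing-safety argument then falls away, and the question is only whether the patient leaves the study.

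4. **Is there a written exception?** None appears in 7.3, 7.3.1, 8.4 or the synopsis. The paragraph in 7.3 refers to each case before a withdrawal and does not set the 7.3.1 cases apart.

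Under either meaning of the word, the texts agree only if the reader supplies a limit on scope that is not on the page.

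**The case against.** The strongest reply is that the sentence was never meant for the stopping criteria. Several withdrawal reasons in 7.3 rest on the Investigator's judgment, and the 7.3.1 criteria are dealt with in their own sentence. The disputed sentence is also conditional, and a listed stopping event can be seen as a case where safety is not assured. In 8.4 it follows the code-breaking text and may mean only that breaking the code does not by itself require withdrawal. These readings are plausible and may be what was intended. Neither is written, so they explain the conflict without removing it.

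A reader might go further than the documents allow in several ways.

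- *A site could keep dosing and be in compliance.* Not established. Continuing would breach the *will* sentence in 7.3, and deviations must be reported (14.6.2). Compliance is contestable, not assured.
- *7.3.1 itself makes every criterion mandatory.* It does not; see step 1 of the working.
- *The drug has a known QT signal, so QTcF is the critical example.* Section 4.2.2 reports some QTc prolongation episodes, 90% of them in oncology studies, without events of clinical concern or a dose-related trend. Sections 7.3.1 and 12.3 separately require interruption when the mean QTcF exceeds 500 msec. Only the later permanent step is in doubt.
- *Early withdrawal loses the biopsy.* Section 9.1.10 waives MRI/MRS and quality of life, not the biopsy. The timing changes.
- *The sentence creates an unblinding problem.* Any platelet-based rule is applied by people who see platelet counts, and 8.4 separates them from the outcome assessors.

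It is also true that relatedness of an SAE or of diarrhea is already a judgment, so those counts would carry some discretion under any wording.

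**Conclusion.** The point holds as a conflict between stated rules on a patient safeguard. It should be corrected. It is more than missing detail, because the two directives point in opposite directions and nothing ranks them.

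Its reach is all six permanent-stop criteria through the wording of 7.3, most sharply the three confirmed blood counts, where *must* also applies. Its effect on the results cannot be sized: the documents do not give the number of patients who met a criterion or were kept on treatment after meeting one. Shifting one patient between categories using the planned arm sizes would be arithmetic, not an estimate.

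The conclusion rests on the text as written, with no limit read into the disputed sentence. If the sponsor confirms that only discretionary withdrawals were meant, the substance is resolved and only the wording remains to be corrected. Nothing here implies a view on which clinical rule is right.

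**What to change.** Reconcile 7.3, 7.3.1, 8.4 and the synopsis:

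- State whether the disputed sentence applies to patients who meet a 7.3.1 permanent-stop criterion. If it does not, limit it in 7.3 and 8.4 to the cases it is meant for.
- State whether *discontinued* there refers to study treatment or to study participation.
- Make *should*, *will* and *must* consistent across the four places.
- If overrides are allowed, record each one and its reason in the eCRF, so that the discontinuation tables can be read alongside them.

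The choice of rule belongs to the sponsor and investigators.

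The cost is one or two sentences in an amendment, the matching word changes and a note to the site(s). No procedures are added, apart from an eCRF entry if overrides are permitted. The SAP (3.5) reports enrollment as complete, so the change guides handling for anyone still on treatment. For the rest, it clarifies how decisions already taken are classified and reported.
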